5.6.3.2. Vital Signs and Physical Examination Findings

Continuous vital sign parameters including temperature (axillary, tympanic or forehead), height, weight, waist circumference, pulse/heart rate, blood pressure (systolic and diastolic), and BMI will be summarized at each assessment time point. BMI will be calculated as weight (kg)/(height (m))², at each time point that body weight is measured. The height measurement collected at Screening Visit S1 will be used in the calculation. Change from baseline will be summarized for the visit of week. Descriptive statistics (mean, standard deviation, median, minimum, and maximum) will be presented. Week 0 is the Baseline visit for the Vital Signs and Physical Examination Findings (for Waist Circumference).

5.6.3.3. Electrocardiogram

Electrocardiogram (ECG) is collected only at Screening Visit S1. Listings will be produced for all ECG data including unscheduled visit data.

5.6.3.4. Other Safety Parameters

Not Applicable

5.7. Other Analyses

5.7.1. Pharmacokinetics

Pharmacokinetics analysis will not be evaluated for this study.

5.7.2. Immunogenicity

Not Applicable.

5.7.3. Pharmacodynamics

All Primary and Secondary endpoints in Section 5.3 and Section 5.4 are analyzed for the Pharmacodynamics endpoint.

5.7.4. Pharmacokinetic/Pharmacodynamic Relationships

Not Applicable.

5.7.5. Biomarkers

Not Applicable.

5.7.6. Health Economics

Not Applicable.

5.7.7. Other Variables and/or Parameters

Coronary Flow Reserve (CFR) screening and screening failure analysis in this study include but not limited to:

- 1. Baseline characteristics of CRF Screening failure vs Included Participants.
- 2. Screening Visit S2 vs Week 0 analysis for:
 - a. Coronary Flow Reserve (CFR).
 - b. Global Longitudinal Strain (GLS).
 - c. carotid-femoral Pulse Wave Velocity (cfPWV).

5.7.8. Definition of Subgroups

The study will be conducted with a subgroup of nicotine users vs. non-nicotine users.

5.8. Interim Analyses

No Interim Analyses will be performed for the study since it terminated prematurely.

5.8.1. Data Monitoring Committee (DMC) or Other Review Board

No DMC will be performed for the study.

6. SUPPORTING DOCUMENTATION

6.1. Appendix 1 List of Abbreviations

AE adverse event

AR[1] First order auto-regression correlation ATC anatomic and therapeutic class

AUDIT Alcohol use disorders identification Test

BMI body mass index BSA body surface area

cfPWV carotid-femoral pulse wave velocity

CFR Coronary Flow Reserve
CI confidence interval
COVID-19 Coronavirus Disease 2019

CV Cardiovascular DBL Database Lock

DLQI Dermatology Life Quality Index
DPS Data Presentation Specifications.

ECG Electrocardiogram FAS Full Analysis Set

GLS Global longitudinal strain

HADS Hospital anxiety and depression scale

HLT High level term
IA Interim Analysis
ICF Informed Consent Form

IGA Investigator's Global Assessment

IQ Interquartile

LOCF last observation carried forward

LSmeans Least Square Means

MACE Major Adverse Cardiovascular Events
MCAR Missing Completely at Random

MedDRA Medical Dictionary for Regulatory Activities
MMRM Mixed-effect model for repeated measures

NRI Non-responder imputation
PASI Psoriasis area and severity index
PSQI Pittsburg sleep quality index
PRO Patient Reported Outcomes

PsA Psoriatic Arthritis
SAE serious adverse event
SAP Statistical Analysis Plan

SC Subcutaneous SD standard deviation

Status: Approved, Date: 21 July 2023

SMQs standardized MedDRA queries TEAE treatment-emergent adverse event

TRTSDT Treatment Start Date
ULN upper limit of normal
WHO World Health Organization

WHO-DD World Health Organization Drug Dictionary

6.2. Appendix 2 Changes to Protocol-Planned Analyses

The Safety Analysis Set is different in the Protocol.

Safety analysis set defined in the protocol as "All enrolled participants who receive at least 1 dose of guselkumab." Whereas in SAP we have modified the definition as "The safety analysis set includes all participants who received at least 1 dose of adenosine and guselkumab".

The Safety Analysis Set will likely contain more participants than the FAS. It would not be appropriate to define the safety analysis set as participants receiving at least one dose of guselkumab. It is necessary to also capture possible safety related information starting with the first assessment of the Coronary Flow Reserve at visit S2, because it involves use of intravenous Adenosine.

All enrolled participants who receive at least 1 dose of guselkumab, while it is "The full analysis set (FAS) includes all participants who received at least 1 dose of guselkumab." in the current SAP.

In Protocol the primary and secondary efficacy endpoints are performed at Week 32 for CFR, GLS and cfPWV, while in SAP it is appropriately defined to be completed at Final Efficacy Visit (Week 32) as per Table 2. The primary and secondary efficacy endpoints will be analyzed at Final Efficacy Visit (Week 32) with the definition applied as per Table 2 for the last dose after premature termination of the study.

In the protocol The Final Efficacy Visit (Week 32) should occur 4 weeks after the last dose of the guselkumab within the study. Whereas in SAP, following the premature termination of the study 4 to 8 weeks after the last dose of guselkumab within the treatment phase will be used.

In the protocol for participants who prematurely discontinues guselkumab before Week 28, the Final Efficacy Visit (Week 32) should take place at the time of discontinuation, or as soon as possible, and all assessments scheduled for the Final Efficacy Visit (Week 32) should be performed, whereas in the SAP for participants who permanently discontinue guselkumab before Week 28, the date of discontinuation will be used.

In the protocol for a Final Safety Visit (Week 40), the participants opting to receive commercially available guselkumab after Week 28, the first dose of guselkumab outside the study (Week 36) should be considered as the Final Safety Visit (Week 40). Whereas in the SAP for Final Safety Visit (Week 40) for participants who receive guselkumab after the treatment phase, the date of the first dose of guselkumab outside of the treatment phase will be used.

The secondary endpoint 'Change from baseline in CFR at Week 16 and Week 32 among participants with CFR in the ranges of 2 to 2.49, 2.5 to 3, and 3.01 to 3.5 at baseline' in the protocol, however a different range of 2 to 2.74 and 2.75 to 3.5 will be used for the final analysis. For the final analysis the study had a low number of participants after premature termination of the study. The ranges were updated accordingly.

Since the study was terminated prematurely the exploratory objectives and endpoints are removed from the corresponding SAP section.

No interim analysis will be performed per the protocol since the study prematurely terminated.

Biomarker analysis will not be performed due to the low number of participants after premature termination of the study.

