ТВ	X		X	X	X	X	X	X	X	X	Specific questions about history of TB or known occupational/personal exposure to individuals with active TB to be asked.
Vital signs	X		X	X	X	X	X	X	X	X	Blood pressure, pulse/heart rate and temperature to be recorded at the dermatology study site prior to Screening Visit S2.
Height	X										
Weight d	X		X			X			X		
12-lead ECG	X										
Pregnancy test e	X	X	X	X	X	X	X	X	X	X	
Injection-site reaction evaluation			X	X	X		X	X			
Clinical Laboratory											
Hematology, chemistry	X		X	X	X	X	X	X	X	X	Laboratory tests are described in Appendix 2.
Lipid and metabolic panel	Х					X			X		Participants must fast (ie, no food or beverages, except water) for at least 8 hours before blood is drawn. Glucose and insulin will be measured as part of this panel.
HbA1c	X					X			X		•
hsCRP	X		X			X			X		
Urinalysis	Х		X			X			Х		If there are signs of proteins and/or glucose on urine test strip, the urine sample must be analyzed centrally, protein and glucose levels must not

Phase	Screening Visit S1 (Dermatology)	Screening Visit S2 (Cardiology)		Tı		ent Pha			Final Efficacy Visit a	Final Safety Visit b	Comments
Week Visit Window (days)	Maximum of 2 weeks prior to Screening Visit S2	Minimum of 2 weeks and maximum of 4 weeks prior to Week 0	0	4 ±	7	16 -7 to +14	20 ±	7	32 -7 to +14	40 ±7	
		to week o									exceed trace levels, one re-test is allowed.
Urine nicotine test f		X	X			X			X		
Efficacy Assessmen	ts										
cfPWV g		X	X			X			X		
GLS g		X	X			X			X		
CFR g		X	X			Х			Х		Must be measured before administration of guselkumab at Week 0. Measured by Transthoracic Doppler Echocardiography with adenosine as vasodilator. CFR should be conducted regardless of a positive urine nicotine test.
PASI	X		X	X	X	X	X	X	X		
BSA	X		X	X	X	X	X	X	X		
IGA	X		X	X	X	X	X	X	X		
PSQI			X			X			X		Paper PROs completed before any other
DLQI			X			X			X		tests, procedures, evaluations, or
HADS (if available)			X			X			X		guselkumab administration on the day of the visit for Week 0 and other scheduled
AUDIT			X			X			X		visits.
Biomarkers											
Serum sample collection			X	X		X			X		Including but not limited to: hsCRP, NT-proBNP, Cytokine-levels including IL-6, IL-17A, IL-17F, IL-22, IL-23, SAA1, SAA2, Olink analysis.
Plasma sample			Х	Х		Х			Х		Concentration of oxidative lipid damage (8-Isoprostane) and malondialdehyde, concentration of antioxidants (Vitamin C and Vitamin E), adipokines (leptin and adiponectin).

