#### Footnotes:

- a. The Final Efficacy Visit should occur 4 weeks after the last dose of the guselkumab within the study. If a participant permanently discontinues guselkumab before Week 28, the Final Efficacy Visit should take place at the time of discontinuation, or as soon as possible, and all assessments scheduled for the Final Efficacy Visit should be performed.
- b. The participant should return for a Final Safety Visit, 12 weeks after the last guselkumab dose. For participants opting to receive commercially available guselkumab after Week 28, the first dose of guselkumab outside the study (Week 36) should be considered as the Final Safety Visit.
- c. Administered at the site by health care professional (HCP) at Week 0. Subsequent doses may be self-administered at the site under supervision up to Week 28.
- d. BMI calculation is done automatically in the eCRF at each time-point when the weight is measured.
- e. Women of childbearing potential who are dosed at the clinic must have a negative serum pregnancy test at Screening Visit S1 and a negative urine pregnancy test at all other visits. Additional serum or urine pregnancy tests may be performed, as determined necessary by the investigator or required by local regulations, to establish the absence of pregnancy at any time during the participation in the study.
- f. Urine nicotine test to be done before any cardiology measurements (cfPWV, GLS and CFR). CFR should be conducted regardless of a positive urine nicotine test.
- g. At the Week 16 and Week 32 visits, participants who have been fasting for the lipid and metabolic panel are permitted to have a non-caffeinated drink prior to the cardiology assessments. Cardiology assessments (cfPWV, GLS, CFR and other assessments) must be performed at the same lab using the same machines and software, and preferably by the same cardiologist/technician at every visit. If CFR measurement is unsuccessful, ie, if the acoustic window of the coronary artery cannot be properly found, 2 attempts to measure a CFR can be made on different days. In such cases, the visit window can be extended by 7 additional days (CFR visit window=-7/+14 days). Guselkumab must not be administered at Week 0 before a CFR measurement is successfully obtained.

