## **Coronary Flow Reserve**

Coronary flow reserve will be measured non-invasively using transthoracic doppler echocardiography,  using a high-resolution ultrasound system with a suitable transducer and the respective software. The acoustic window will be around the midclavicular line in the fourth and fifth intercostal spaces in the left lateral decubitus position. Long-axis views of the left ventricle will be obtained, and the ultrasound beam will then be angled laterally and superiorly to image the anterior interventricular groove. The coronary blood flow in the distal portion of the left anterior descending artery (LAD) will be examined with the help of color Doppler flow mapping. A sample volume will be positioned on the color signal in the LAD, and Doppler spectral tracings of flow velocity will be recorded. First, the baseline spectral Doppler signals in the distal portion of the LAD will be recorded. Then 140 µg/kg/min adenosine, a coronary vasodilator, will be administered for 5 minutes. Doppler signals will be recorded continuously at baseline and during the period of adenosine infusion. Measurements of hyperemic coronary flow velocity will be done continuously during the adenosine infusion, and the CFR measurement will be recorded based on the guidelines provided by the cardiology core lab.

Cardiac parameters, along with strain and coronary parameters will be assessed by the cardiology core lab as defined in the process document of the core lab.

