4. POPULATIONS (ANALYSIS SETS) FOR ANALYSIS

Analysis Set	Description
Screened	All participants who signed the informed
	consent form (ICF).
Full Analysis Set (FAS)	The FAS includes all participants who
	received at least 1 dose of guselkumab.
Safety Analysis Set	The safety analysis set includes all
	participants who received at least 1 dose of
	adenosine and guselkumab.

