5.6. Other Safety Analyses

All safety analyses will be based on the safety analysis set based on actual intervention received, unless otherwise specified.

Missing safety data will generally not be imputed. Safety assessment values of the form of "<x" / " \le x" (ie, below the lower limit of quantification) or "> x" / " \ge x" (ie, above the upper limit of quantification) will be imputed as "x" in the calculation of summary statistics but displayed as "<x" / " \le x" or ">x" / " \ge x" in the listings.

For all continuous safety variables, descriptive statistics by Nicotine use, non-Nicotine use and Total group will include the N, mean, standard deviation, median, minimum, and maximum. Categorical variables will be summarized by Nicotine use, non-Nicotine use and Total group using frequency counts and percentages.

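### The SAP's Safety Analysis Set requires both adenosine and guselkumab, so it cannot exceed the FAS and contradicts the SAP's own reason for changing it

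*SAP*

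**What the plan says.** Protocol Section 9.3 bases both the FAS and the Safety Analysis Set on at least one guselkumab dose. SAP Section 4 keeps that basis for the FAS but requires at least one dose of "adenosine and guselkumab" for the safety set. SAP Appendix 2 (Section 6.2) repeats the definition and presents it as a deliberate change: "The safety analysis set includes all participants who received at least 1 dose of adenosine and guselkumab".

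Appendix 2 then gives its reasons. It expects that "The Safety Analysis Set will likely contain more participants than the FAS". It adds: "It would not be appropriate to define the safety analysis set as participants receiving at least one dose of guselkumab". It also explains that safety information has to be captured from the first CFR assessment at S2, because that assessment uses intravenous adenosine.

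SAP Section 5.6 makes the set the default: "All safety analyses will be based on the safety analysis set based on actual intervention received, unless otherwise specified". The treatment-emergent definition in SAP Section 5.6.2 opens at adenosine or at first guselkumab, so it joins the two agents with 'or'.

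**The concern.** The definition and its stated reason describe different populations. The reason calls for a set wider than the FAS, reaching back to the first infusion. The definition narrows the FAS or leaves it unchanged.

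The people at issue are those who received adenosine only because of the study and were then never given guselkumab. Examples are participants whose CFR was out of range at S2 or Week 0, or who left before dosing. For Appendix 2's expectation to come true, this is the group the change has to add. If a programmer codes the definition as it stands, reportable AEs in this group have no place in analyses run on the default safety population.

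**Working it through.** The plan gives no figure to reproduce, only a stated size relation: safety set larger than FAS. The check is set logic.

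**Inputs**
- FAS: at least one guselkumab dose (SAP Section 4).
- Safety set: at least one dose of adenosine and guselkumab (SAP Section 4, Appendix 2).
- CFR uses adenosine. Protocol Schedule of Activities, CFR row: "Measured by Transthoracic Doppler Echocardiography with adenosine as vasodilator". Protocol Section 8.1.1, on the procedure: "adenosine, a coronary vasodilator, will be administered for 5 minutes".
- Order of procedures, Schedule of Activities, footnote g: "Guselkumab must not be administered at Week 0 before a CFR measurement is successfully obtained".

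**Step 1: the definitions.** Let A be everyone with at least one adenosine dose and G everyone with at least one guselkumab dose. Then FAS = G and the written safety set is A ∩ G. Since A ∩ G is contained in G, N(safety) ≤ N(FAS) always.

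**Step 2: the four exposure patterns**

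| Adenosine | Guselkumab | In FAS | In safety set as written ('and') | In safety set with 'and/or' |
|---|---|---|---|---|
| no | no | no | no | no |
| no | yes | yes | no | yes |
| yes | no | no | no | yes |
| yes | yes | yes | yes | yes |

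No pattern is in the written safety set and outside the FAS. The adenosine-only row, the one that could make the safety set larger, is excluded.

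**Step 3: compliant dosing.** Guselkumab requires a prior CFR, and CFR requires adenosine, so G is contained in A. Hence A ∩ G = G = FAS. This is the guselkumab-only set that Appendix 2 rejects. The guselkumab-only row of the table can arise only through a dosing deviation, and it makes the written set smaller than the FAS.

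**Step 4: the union.** Under compliant dosing, N(A ∪ G) = N(A) = N(FAS) + k, where k is the number infused but never dosed. Appendix 2's expectation is met under the union whenever k is at least 1. Under the intersection it cannot be met.

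**Step 5: can k be above zero?** The design allows it. CFR must be from 2 to 3.5 at both S2 and Week 0 (Protocol Section 4.1), so the infusion comes before the eligibility decision it informs. SAP Section 5.7.7 plans a comparison of CFR screen failures with included participants. SAP Section 5.2 also has a listing category for those enrolled but not dosed, although it may turn out empty. No document gives k.

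**Step 6: effect of a union on percentages.** An on-guselkumab count x that reads x / N(FAS) would read x / (N(FAS) + k), smaller by the factor N(FAS) / (N(FAS) + k). This matters because SAP Appendix 5 takes medication percentages on the safety set, and SAP Section 5.6.1 comes under the same default through Section 5.6. The guselkumab-treated denominator therefore has to be stated for those summaries.

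**The case against.** The strongest reply is that this is a one-word slip which the surrounding text largely resolves. Appendix 2 states the intended direction straight after the definition. The TEAE definition uses 'or'. SAP Section 5.6.1 reports the percentage who received guselkumab, which would be 100% by construction under the intersection. SAP Appendix 3 reports the size of each analysis set, so equality with the FAS would be visible. All of this supports a union as the intent. It does not change the operative definition, which reads the same way in two places.

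Four stronger readings are tempting, and the documents do not support them.

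- *AEs in never-dosed participants are lost or have no output.* Protocol Section 8.3.1 collects AEs from consent, and serious events go to the sponsor. SAP Section 5.6.2 says that all reported TEAEs are analysed and promises a listing of all SAEs. Whether Section 5.6 restricts those outputs to the safety set is arguable, so some of these events may appear. For participants later dosed, events between S2 and Week 0 are already covered. Usual adenosine effects are not AEs at all.
- *The secondary AE endpoint has the wrong denominator.* It concerns guselkumab-treated participants (SAP Section 5.4.1), and that population is right for it.
- *The SAP gives adenosine-only participants no end to the TEAE window.* Section 5.6.2 refers to the last dose without naming the agent, and SAP Section 4 itself speaks of a dose of adenosine. The end is ambiguous, not absent.
- *The omission can be quantified.* Neither the number infused nor the share never dosed is stated, so any count or precision figure would rest on assumption alone.

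**Conclusion.** The contradiction stands with high confidence and rests on the SAP's wording and the protocol's order of procedures alone. As written, the Safety Analysis Set is never larger than the FAS and equals it under compliant dosing, so Appendix 2's rationale cannot be met. Read literally, participants infused at S2 or Week 0 but never dosed are outside the default safety population.

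The size is k, which the documents do not give and which could be small. No efficacy analysis is affected, and the guselkumab AE endpoint stays as it is. This should be corrected because the definition determines a population flag, but it does not threaten the trial's conclusions.

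One neighbouring issue is separate and minor. For an AE with missing onset that resolved before first guselkumab, SAP Section 5.6.2 implies it is not treatment-emergent, while Section 5.6.2.1.1 implies that it is. Those two rules should be reconciled in their own right.

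**What to change.** 1. In SAP Section 4 and Appendix 2, define the Safety Analysis Set as participants with at least 1 dose of adenosine and/or guselkumab.
2. Keep guselkumab-treated participants as the stated denominator for the secondary AE endpoint (Section 5.4.1) and for on-guselkumab summaries, including exposure (Section 5.6.1) and concomitant medication (Appendix 5).
3. Show AEs in adenosine-only participants in their own table or listing.
4. In Section 5.6.2, say which agent the last dose refers to, so that the TEAE window has a clear end for adenosine-only participants.

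The cost is SAP wording, one population flag and one extra AE table or listing. No new data collection is needed if AEs were recorded from consent as Protocol Section 8.3.1 requires. SAP Appendix 6 speaks of documenting conditions as AEs from the Baseline visit onward, so it is worth confirming that events from S2 were recorded.

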6.3. Appendix 3 Demographics and Baseline Characteristics

The number of participants in each analysis set will be summarized and listed by Nicotine user, Non-nicotine user and overall. In addition, the distribution of participants by country, and site ID will be presented unless otherwise noted.

Table 3 presents a list of the demographic variables that will be summarized by Nicotine user, Non-nicotine user and total for the FAS.

Similarly, baseline characteristics, including Years of Plaque Type Psoriasis Diagnosis, IGA Score, PASI Score, PsA and Cardiologic Family History, Psoriatic arthritis present, Prior nonbiologic systemic therapy, Prior biologic systemic therapy, Dyslipidemia/hyperlipidemia, hypertension, and Nicotine use status ([Never, Former, and Current]). will be summarized by Nicotine user, non-nicotine user and total for the FAS. Years of Psoriasis Plaque Type Diagnosis is defined as Year of baseline assessment – Year of first onset of plaque type psoriasis, as collected in the CRF.

Table 3: Demographic Variables

Continuous Variables:	Summary Type		
Age (years)			
Weight (kg)			
Height (cm)	Descriptive statistics (N, mean,		
BMI (kg/m²)	standard deviation [SD], median		
Waist circumference (cm)	and range [minimum and		
BSA (%)	maximum], and IQ range).		
Baseline PASI			
Time since plaque type psoriasis diagnosis in years			
Categorical Variables			
Age ([<45 years and >= 45 years])			
Sex (male, female, undifferentiated)			
Race (White, Black, Asian, Other)			
BMI ([underweight <18.5 kg/m², normal 18.5-<25 kg/m², overweight 25-			
$<30 \text{ kg/m}^2, \text{ obese } >=30 \text{ kg/m}^2]$			
Psoriatic arthritis present	Engagement distribution with the		
PsA family history	Frequency distribution with the number and percentage of		
Cardiologic family history	participants in each category.		
Dyslipidemia/hyperlipidemia	participants in each category.		
Baseline IGA score (0 = clear, 1 = almost clear, 2 = mild, 3 = moderate and			
4 = severe.)			
Hypertension			
Nicotine use status ([Never, Former, Current])			
Prior nonbiologic systemic therapy			
Prior biologic systemic therapy			

A listing of prior topical therapy and phototherapy or systemic therapy for Psoriasis will be provided.

